[figure not shown]
Statistical Analysis Plan

Implementation Evaluation of a Combination Intervention for Sustainable Blood Pressure Control in Rural KwaZulu-Natal, South Africa

ClinicalTrials.gov registration Number: NCT05492955

Version: 1.0

Date: 20 October 2023

Written by:		Role:	Date:
Name	[name]	Trial statistician	
Signature			23 October 2023
Authorised by:			
Name	[name]	Head, Data Science Unit	
Signature			
Name	[name]	Co-PI	23 October 2023
Signature			
Name	[name]	Co-PI	24 October 2023
Signature			

1. Overview of trial design & aims

IMPACT-BP is a randomised controlled trial to evaluate the effectiveness of community-based, technology-supported interventions to reduce systolic blood pressure (SBP) and improve blood pressure control among individuals with uncontrolled hypertension in rural KwaZulu-Natal. The study aims to identify the optimal strategy for blood pressure management in rural South Africa.

The study will compare three treatment strategies: 1) standard of care (SOC), clinic-based management of hypertension, 2) a community blood pressure monitor-based model, in which individuals receive blood pressure cuffs, and are remotely monitored by nurses via community blood pressure monitors (CBPM) and a mobile health-based clinical decision support tool, and 3) an enhanced community blood pressure monitor-based model that includes home-based blood pressure cuffs that transmit readings over cellular networks directly to clinic-based nurses (eCBPM+). In both intervention groups, CBPMs will visit participants to record (CBMP) or verify (eCBPM+) blood pressure readings, dispense medications, and relay instructions from clinic nurses.

2. Study endpoints

The trial aims will be evaluated through the primary and secondary outcomes below, as defined in the study protocol.

Primary outcome

- Difference between arms in change from baseline in systolic blood pressure 6 months after enrolment.

Secondary outcome

- Proportion of participants with blood pressure control at 6 after enrolment (defined as systolic blood pressure <140 mmHg and diastolic blood pressure <90 mmHg)

Safety measures

- Number of adverse drug reactions.
- Proportion of participations retained in hypertension care at 6 months.

Acceptability, fidelity, sustainability, and cost-effectiveness of the interventions will also be assessed; these objectives will be covered in a separate analysis plan.

3. Eligibility criteria

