For participants who cannot be reached to schedule 6 or 12 month visits, a study staff member will attempt a home visit to collect outcome data.

6. Sample size

Based on patient attendance data from the two PHCs in our study in 2020, we estimate that there are over 1000 individuals with uncontrolled hypertension and thus eligible to enrol in the trial. We anticipate mean blood pressure at baseline will be 150/95 mmHg, with a standard deviation (SD) of 19 mmHg, based on previous studies. With 774 participants enrolled (258 per arm), we will have 80% power to detect a 5 mmHg difference between arms in the change of blood pressure from baseline to 6 months, assuming 20% loss to follow-up, a correlation between baseline and follow-up measurements of 0.5, and an alpha of 2.5% to account for multiple testing with comparisons between the SOC and both intervention arms (Table 1).

This same sample size will also give us greater than 80% power to detect an increase in the proportion of participants who achieve BP control (defined by a systolic BP <140 mmHg and diastolic BP <90mm Hg) at 6 months from 30% in the SOC arm to 45% in the interventions arms, or from 40% in the SOC to 56% in the intervention, also allowing for an alpha of 2.5% to account for multiple testing.

Table 1. Differences in change from baseline that can be detected with 80% power

N enrolled per arm	Loss to follow-up	Difference that can be detected (mmHg)	Standard deviation	Correlation between observations	Power
330	20%	5.0	19.0	0.20	80%
258	20%	5.0	19.0	0.50	80%
148	20%	7.5	19.0	0.20	80%
115	20%	7.5	19.0	0.50	80%

7. Definitions and analysis populations

All analyses will be conducted using the intention-to-treat principle, where all randomised participants will be included in the analysis regardless of adherence to the intervention.

All analyses of blood pressure will use the average of the second and third measurement as the blood pressure measurement for that visit. In the primary analyses, participants who are missing any of the three measurements will be considered to be missing blood pressure data for that visit. As a sensitivity analysis, individuals with fewer than three measurements will be included, using the average if there are two, or a single measurement if only one is available.

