The baseline characteristics of participants who are included in the analyses at 6 months (primary outcome) and 12 months and those who are not included (either because they withdrew, were lost to follow-up, or missed the relevant visit) will be summarised and compared descriptively.

9. Statistical methods

The statistical methods that will be used to address each study objective are described below. To correct for multiple testing when comparing the two intervention groups with the control group (SOC), we will use the Bonferroni correction with a significance p-value of 0.025

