9.1 Primary objective

The primary objective of the trial is to examine the effect of the interventions on the change from baseline in systolic blood pressure 6 months after enrolment. The mean

and SD systolic blood pressure, and the mean and SD change from baseline, at the 6 and 12 month visits will be summarised by treatment arm.

Linear regression will be used to estimate the mean difference, and its 95% confidence interval (CI), between each intervention and SOC (i.e. CBPM vs SOC and eCBPM+ vs. SOC) in the change from baseline at 6 months. The response variable will be systolic blood pressure at 6 months; the model will include treatment arm, clinic, active use of hypertension medication and baseline systolic blood pressure.

In secondary exploratory analyses, we will adjust for baseline values of age, sex, body mass index (BMI), smoking status and HIV. In separate models, we will fit an interaction term between the treatment arm and sub-groups of interest (e.g. sex, age group, co-morbidities) to examine sub-group effect sizes and potential effect modification.

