9.2 Secondary objective

The secondary objective of the trial is to examine the effect of the interventions on the proportion of participants with controlled blood pressure 6 months after enrolment.

The number and proportion of participants with controlled blood pressure (defined as systolic blood pressure <140 mmHg and diastolic blood pressure <90 mmHg) at the 6 and 12-month visits will be tabulated by treatment arm. Logistic regression will be used to estimate the odds ratio (OR) and 95% CI for the effect of each intervention on blood pressure control, compared with SOC. The model will include terms for treatment arm, use of hypertension medication, and clinic [randomisation strata].

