9.3 Safety measurements

The number and proportion of participants with at least one adverse event (AE), and the total number of AEs, will be tabulated by the treatment arm. AEs will be tabulated by diagnosis, severity and relationship to the intervention.

The number and proportion of participants who are still in hypertension care 6 months after enrolment will be tabulated by the treatment arm. Retention in care will be defined as currently having sufficient BP medicine in possession (taking into account the date of last visit and the amount of medication dispensed), as the primary definition. As a secondary definition, retention will be defined as having seen a health care worker for

hypertension in the past 3 months. Logistic regression will be used to estimate the OR and 95% CI for the effect of each intervention on retention in hypertension care. The model will include terms for treatment arm, clinic and active use of hypertension medication at baseline.

10. Additional exploratory analyses

The effect of each intervention (vs SOC) on mean change from baseline in systolic blood pressure over 12 months will be estimated using a linear mixed model. The response variable will be systolic blood pressure (at 6 and 12 months); the model will include fixed effects for treatment arm, visit, a treatment arm-visit interaction term, randomisation strata (clinic and active use of hypertension medication at enrolment) and baseline systolic blood pressure, and participant as a random effect to account for correlation of repeated measurements within the participant. The inclusion of the interaction term allows the effect of the intervention to differ over time. If the interaction term is not statistically significant at $p < 0.10$, we will drop it from the model and estimate the overall effect of each intervention (vs SOC) on the change in systolic blood pressure during the trial.

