The effect of each intervention (vs SOC) on blood pressure control over 12 months will be estimated using random effects logistic regression. The model will include fixed effects for treatment arm, visit, randomisation strata (clinic and active use of hypertension medication at enrolment) and treatment arm-visit interaction term, and random effects for the participant to account for correlation of repeated measurements. If the interaction term is not statistically significant at $p < 0.10$, we will drop it from the model and estimate the overall effect of each intervention on the blood pressure control pressure during the trial.

All participants with outcome data at either follow-up visit will be included in these analyses. Estimates from random effects models are valid under the assumption that the outcome data are missing at random conditional on the observed outcome at the non-missing visits, and other covariates in the model.

For participants with missing outcome data at month 6 or month 12, we may impute blood pressure measurements at those time points, using multiple imputation by

chained equations. Imputation models will contain observed blood pressure measurements, age, sex, BMI, smoking status, use of anti-hypertensive medication, HIV, clinic, treatment group and any covariates that are found to be associated with missingness.

The consistency of the effect of the intervention on the primary outcome will be assessed in the following pre-specified groups, using a statistical test of interaction. Effect estimates and 95% confidence intervals will be presented for each subgroup, plus the interaction p-value.

- Individuals with systolic blood pressure (SBP) ≥ 160 mmHg and those with SBP < 160 mmHg at enrolment.
- Individuals based on self-reported HIV status.
- Men and women
- Individuals aged ≥ 60 years and < 60 years.

References

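### The SAP tests each SOC contrast at 0.025 but reports unlabelled 95% intervals, and it plans no eCBPM+ versus CBPM estimate although the stated aim is the optimal strategy

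*SAP*

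**What the plan says.** **Test level.** SAP section 9 sets the rule for comparing the two intervention groups with SOC: "we will use the Bonferroni correction with a significance p-value of 0.025". SAP section 6 sizes the trial the same way, with "an alpha of 2.5% to account for multiple testing with comparisons between the SOC and both intervention arms", and applies 2.5% again to blood pressure control.

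**Interval level.** SAP 9.1, on the primary outcome: "Linear regression will be used to estimate the mean difference, and its 95% confidence interval (CI), between each intervention and SOC". SAP 9.2, on the secondary outcome: "Logistic regression will be used to estimate the odds ratio (OR) and 95% CI for the effect of each intervention on blood pressure control". Neither section gives a 97.5% interval or says that the 95% intervals are unadjusted for the two comparisons.

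**Contrasts.** SAP 9.1 spells out which comparisons are meant: "i.e. CBPM vs SOC and eCBPM+ vs. SOC) in the change from baseline at 6 months". SAP 9.2 compares each intervention with SOC. The two 12-month models in SAP section 10 do the same: "The effect of each intervention (vs SOC) on mean change from baseline in systolic blood pressure over 12 months" and "The effect of each intervention (vs SOC) on blood pressure control over 12 months".

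**Aim.** SAP section 1: "The study aims to identify the optimal strategy for blood pressure management in rural South Africa". The Aim 2 overview in the protocol (V.A) says the same in nearly the same words. The primary endpoint in both documents, and the protocol's Aim 2 analysis plan (V.L), speak only of a difference between arms and do not name the contrasts.

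**The concern.** There are two separate points, and the second carries more weight.

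1. A test at 0.025 corresponds to a 97.5% interval. When p lies between 0.025 and 0.05, the reported 95% interval excludes no effect while the stated threshold is not met. Readers commonly go by the interval, and here it can suggest an effect that the SAP's own rule does not declare.

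2. Choosing between two programmes needs a comparison of the two. Two tests against SOC do not supply it. If both pass, they give no ranking. If one passes and the other does not, that alone does not show that the programmes differ. With no direct contrast named, the programmes are likely to be ranked by which one passed. A direct contrast added later would be chosen with the results in view.

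**Working it through.** **Inputs** (SAP section 6; protocol Table 2 for the evaluable number): SD 19 mmHg, baseline to follow-up correlation 0.5, 258 enrolled and 206 evaluable per arm, alpha 2.5%, target difference 5 mmHg, control rates of 30% (SOC) and 45% (interventions). Sidedness is not stated. I take it as two-sided because that reproduces the plan's number.

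**Plan's own figure.** Baseline-adjusted residual SD = 19 × √(1 − 0.5²) = 16.45. Evaluable n per arm = 2 × (2.241 + 0.842)² × 16.45² / 5² = 205.9, so 206. Enrolled = 206 / 0.80 = 257.5, so 258 per arm and 774 in total. This agrees exactly.

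**Interval against test, systolic pressure.**
- SE of any pairwise difference = 16.45 × √(2/206) = 1.62 mmHg.
- 95% half-width = 1.960 × 1.621 = 3.18 mmHg; 97.5% half-width = 2.241 × 1.621 = 3.63 mmHg; ratio 1.14.
- Interval and test therefore disagree for observed differences between 3.18 and 3.63 mmHg.

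The chance of landing there for one contrast is the power at 0.05 minus the power at 0.025. The chance for at least one of the two contrasts comes from simulated three-arm trials with a shared SOC arm.

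| True effect in both programmes | One contrast | At least one contrast |
|---|---|---|
| 5 mmHg | 86.9% − 80.0% = 6.9% | 13% |
| 3 mmHg | 10.9% | 20% |
| 0 | 5.0% − 2.5% = 2.5% | 4.9% |

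**Interval against test, blood pressure control.** These figures use an unadjusted Wald log odds ratio with 206 per arm. With SOC observed at 30%, the zone runs from 39.2% to 40.6% controlled (odds ratio 1.50 to 1.59). At true rates of 30%, 45% and 45%, a given contrast lands there in 6.6% of trials and at least one does in 12%.

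**Ranking by tests against SOC, systolic pressure.** The documents give no expected difference between the two programmes, so the unequal pairs are illustrative.

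| True effects (mmHg) | Exactly one passes 0.025 | Direct 95% CI includes 0, among those |
|---|---|---|
| 5 and 5 | 23% | 86% |
| 5 and 3 | 50% | 61% |
| 5 and 2 | 65% | 40% |

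At 5 and 5 both programmes pass in 69% of trials. For blood pressure control at 30/45/45%, exactly one passes in 21%, and the direct interval includes an odds ratio of 1 in 85% of those.

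**What a direct contrast would deliver.**
- Systolic pressure: 95% half-width 3.18 mmHg, the same as against SOC, because the arms are of equal size. Power at two-sided 0.05 is 46% for a true 3 mmHg and 87% for 5 mmHg.
- Blood pressure control, both arms near 45%: the 95% limits are the odds ratio divided and multiplied by exp(1.96 × √(2 / (206 × 0.45 × 0.55))) = 1.47. Power for 45% against 55% is about 54%.

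**The case against.** **On the intervals.** A 95% interval for estimation beside a Bonferroni threshold for decision is a coherent plan. The SAP states the threshold ahead of all its objectives and nowhere says that the interval decides. That stands: error control is intact and no formal conclusion changes. The 13% and 20% also include trials in which the other programme has already passed. A contrast falls in the zone with neither programme passing in 4.0% of trials at 5 and 5 mmHg, and in 12.1% at 3 and 3. With no true effect the rate is 2.5% per contrast. Taken alone this is a minor point, and a single label would settle it.

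**On the direct contrast.** The design is two programmes against a control, and alpha and sample size were built for that. The optimal strategy is named in an overview sentence, not as an endpoint, and the SAP's endpoint wording (difference between arms) does not exclude the direct comparison. Acceptability, fidelity, sustainability and cost-effectiveness also bear on what is optimal. They are left to a separate plan, and the protocol says cost-effectiveness will also be calculated for each arm. Arm means and SDs will be tabulated, and a reader could approximate the direct interval closely: in a simulation check, the SE rebuilt from the SOC results and arm sizes was within 0.5% of the model SE in 95% of trials.

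Much of this is fair, but it does not close the gap. SAP 9.1 itself narrows the endpoint wording to the two SOC contrasts. The protocol describes cost-effectiveness as compared with standard of care and names no direct 6-month systolic contrast. An interval rebuilt by a reader has no pre-specified status. That the programmes would be ranked by which one passed is a judgement about how results get read, not something the plan proposes.

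**Conclusion.** The concern holds on both points, and the SAP should be changed. Nothing here undermines the 0.025 tests, the family-wise error for the two SOC contrasts, or the sample size.

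The missing direct contrast is the main point. The plan states an aim that its listed comparisons do not address, although the planned models can already supply the estimate. The 86% figure rests on exactly equal true effects of 5 mmHg; it falls to 61% and 40% under the unequal pairs, so its size depends on that assumption. That both programmes can pass and remain unranked (69% at 5 and 5 mmHg) is a further reason for naming the contrast.

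The mismatch of interval and test is the lesser point: a band 0.46 mmHg wide (3.63 − 3.18, from unrounded values).

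The systolic figures assume SD 19 mmHg, correlation 0.5 and 206 evaluable per arm. The blood pressure control figures are unadjusted approximations to the planned logistic model.

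**What to change.** 1. Keep Bonferroni. In SAP 9.1 and 9.2, report 97.5% intervals for the two SOC contrasts on systolic pressure and on blood pressure control. Label any 95% intervals shown as not adjusted for the two comparisons.
2. Pre-specify the eCBPM+ minus CBPM difference in 6-month systolic pressure, and the matching odds ratio for control, each with a 95% interval from the regression model already planned. Name it a secondary contrast outside the alpha family, to be read as an estimate and reported whatever the SOC results are.
3. State its power at alpha 0.05 for illustrative differences (46% at 3 mmHg and 87% at 5 mmHg; about 54% for 45% against 55% controlled). Say that an interval including 0, or an odds ratio of 1, is not evidence of equivalence.
4. Say that cost-effectiveness and implementation outcomes, in the separate plan, also inform which strategy is optimal.

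The cost is SAP wording and one extra contrast from each planned model, with no new data and no change to tests or sample size. The 97.5% intervals are about 14% wider (±3.63 against ±3.18 mmHg). Making the direct contrast a third Bonferroni test is not advised: at 0.05/3, power for 5 mmHg with 206 evaluable per arm falls from 80.0% to 75.5%, and restoring 80% would take 284 enrolled per arm (852 in total). If the sponsor does not want the contrast, the alternative is to narrow the optimal-strategy wording to effectiveness against SOC.

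### The Bonferroni rule at 0.025 is valid and meets its stated power, but Holm's step-down rule would give more power to confirm both programmes at the same 5% family-wise error

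*SAP*

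**What the plan says.** SAP section 9 opens with one multiplicity rule for comparing the two intervention groups with SOC: "we will use the Bonferroni correction with a significance p-value of 0.025". Section 9.1 identifies the two primary comparisons ("i.e. CBPM vs SOC and eCBPM+ vs. SOC") and reports each as a mean difference with a 95% confidence interval, from a linear regression of 6-month systolic pressure that includes baseline systolic pressure.

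SAP section 6 uses the same threshold for the sample size: "an alpha of 2.5% to account for multiple testing with comparisons between the SOC and both intervention arms". The design claim is "80% power to detect a 5 mmHg difference between arms in the change of blood pressure from baseline to 6 months". Section 6 also applies the 2.5% alpha to the secondary outcome, blood pressure control at 6 months. The sample-size text in Protocol section V.J gives the same figures and does not name a correction. Neither document mentions a step-down, hierarchical or Dunnett-type procedure.

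**The concern.** Under plain Bonferroni the second comparison is still held to 0.025 after the first has succeeded. Once one null hypothesis has been rejected, only one remains that could be rejected in error, so the full 5% can be spent on it. Holm's rule does this: the smaller p-value is tested at 0.025 and, if it passes, the other at 0.05.

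The trial is meant to find the best of three strategies. The two programmes share home visits, nurse review and the decision-support algorithm, and differ mainly in how readings reach the nurse. The power statement for blood pressure control assumes a benefit in both. Both working is therefore a central planning scenario, and it is the one where plain Bonferroni gives most away.

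**Working it through.** **Inputs, all from SAP section 6.** Difference 5 mmHg; SD 19 mmHg ("with a standard deviation (SD) of 19 mmHg, based on previous studies"); "a correlation between baseline and follow-up measurements of 0.5"; 258 enrolled per arm, 774 in total; "assuming 20% loss to follow-up"; alpha 0.025 per comparison. Sidedness is not stated. Two-sided is inferred because it reproduces the plan's figure; one-sided 0.025 would give 171 evaluable and 214 enrolled per arm.

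**Reproducing the plan's figure.** Because the model adjusts for baseline, the residual SD is 19 × √(1 − 0.5²) = 16.45, with variance 361 × 0.75 = 270.75.

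n = 2 × 270.75 × (2.2414 + 0.8416)² / 5² = 205.9, so 206 evaluable per arm. Then 206 / 0.8 = 257.5, so 258 enrolled, and 3 × 258 = 774. The plan's figure reproduces.

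**Joint distribution of the two tests.** Standard error = 16.45 × √(2/206) = 1.621, so a 5 mmHg effect has expected z = 5 / 1.621 = 3.084. The comparisons share the SOC arm. With equal numbers per arm, their correlation is (σ²/n) / (2σ²/n) = 0.5.

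**Decision rules.** Bonferroni rejects a comparison if |z| > 2.241. Holm also rejects it if |z| > 1.960 and the other comparison has |z| > 2.241.

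**Both effects 5 mmHg.**
- Bonferroni, per comparison: Φ(3.084 − 2.241) = 80.0%.
- Bonferroni, both: 68.8% from the bivariate normal.
- At least one, either rule: 2 × 80.03 − 68.75 = 91.3%.
- Trials where one comparison passes 0.025 and the other has p between 0.025 and 0.05: 9.1%.
- Holm, both: 68.8 + 9.1 = 77.9%.
- Holm, per comparison: 80.0 + 9.1/2 = 84.6%.

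A simulation of 2,000,000 pairs of z-statistics agrees to within 0.1 percentage point.

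**Other scenarios.** The documents give no unequal effects. The values 3 and 2.5 mmHg are assumptions used to show a range.

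| True effects (mmHg) | Quantity | Bonferroni | Holm |
|---|---|---|---|
| 5 and 3 | power, weaker arm | 35% | 44% |
| 5 and 2.5 | power, weaker arm | 24% | 33% |
| 5 and 0 | power, effective arm | 80.0% | 80.2% |
| 5 and 0 | null arm falsely declared effective | 2.5% | 4.2% |
| 0 and 0 | any false declaration | about 4.6% | about 4.6% |

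As the effect in the other arm becomes very large, Holm's false-declaration rate for a null arm approaches 5.0%.

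**Why Holm controls the error.** If both nulls are true, a false rejection needs at least one p ≤ 0.025, which has probability at most 2 × 0.025 = 5%. If only one null is true, it can be rejected only when its own p ≤ 0.05, again at most 5%. Neither step uses the correlation.

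**Secondary outcome.** With 206 per arm at alpha 0.025, power is 82.0% for 30% versus 45% and 84.7% for 40% versus 56%, consistent with the plan. A test at 0.05, which is Holm's second step, would have 88.5% and 90.4%.

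**The case against.** The strongest reply is that nothing is wrong with the plan. Bonferroni is valid, agrees with the sample-size alpha and delivers the promised 80% per comparison; the documents promise no particular power to win both. All of that stands. A reader might infer that the plan contains an error or that the trial is underpowered. The documents support neither.

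A reader might also infer that Holm raises the chance of a positive trial or justifies enrolling fewer people. The chance of at least one success does not change. Holm would reach 80% per comparison with about 184 evaluable per arm (230 enrolled), but only if both arms truly have a 5 mmHg effect. If one works, the full 206 are still needed.

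Three further objections carry weight:
- The higher false-declaration rate for a null arm is a real cost, although it stays below 5%.
- Bonferroni pairs directly with 97.5% intervals and Holm has no equally simple match. Whenever Holm adds a rejection, the 97.5% interval includes the null. At 5 and 5 mmHg this is 9.1% of trials, which is the whole gain in confirming both. It weighs less here because the SAP's 95% intervals already do not match its 0.025 threshold.
- Dunnett-type methods could use the correlation that Holm ignores. Holm is not the only improvement; its advantage is that it needs no assumption about that correlation.

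**Conclusion.** The point holds as an inexpensive, optional gain in efficiency. With both programmes truly at 5 mmHg, Holm adds about 4.6 percentage points of power per comparison and about 9 points for confirming both. The chance of missing at least one effective programme falls from about 31% to 22%. The gain is 0.2 points or less for the effective arm if only one works, and zero for winning at least one comparison.

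The power figures rest on the plan's SD, correlation and loss to follow-up, on two-sided tests, and on equal evaluable numbers per arm. The 5% error control does not depend on these power inputs; it needs only valid p-values.

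**What to change.** In SAP section 9, replace the Bonferroni sentence with Holm: test the smaller of the two p-values at 0.025 and, if it passes, the other at 0.05. Apply this separately within the primary outcome and within blood pressure control. Changing only the primary comparisons would leave the secondary ones without the rule that section 6 assumes. If the opening sentence is also meant to cover the retention comparison in section 9.3, apply the same rule to that pair. As now, the 5% is then controlled within each outcome and not across outcomes.

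Report 97.5% intervals as conservative companions, and state that when the second p-value lies between 0.025 and 0.05 the interval will include the null although Holm rejects. Leave the sample size and its 2.5% alpha as stated; they describe the first step and are conservative for the second.

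The cost is a few sentences, subject to timing. The SAP is version 1.0, with signatures dated 23 and 24 October 2023, and Holm is the more liberal rule. It should be adopted by dated amendment before any data are examined by arm, in line with Protocol section V.L and with the lock-and-sign condition in SAP section 7. If arm-level outcomes have already been seen, the signed Bonferroni rule should stand.
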